### 9. RESEARCH METHODS

#### 9.1. Study Design

This structured secondary data collection study will be a retrospective cohort study using Centers for Medicare and Medicaid Services (CMS) Medicare data to examine the effect of PCV13 receipt on the risk of MACE among adults aged  $\geq 65$  years in the United States. Individuals will be identified using Medicare Fee-for-Service (FFS) Parts A and B enrollment and claims data.

The analysis will be conducted at the time-segment level using a target trial emulation approach. In this time-segment design, individuals who receive a PCV13 vaccine during the study period can contribute up to two time segments during the follow-up period: a PCV13 unvaccinated time segment and a PCV13 vaccinated time segment. Each segment will be attributed to the appropriate vaccination exposure status cohort, resulting in the individual having two separate index dates included in the analysis. Inclusion/exclusion criteria and baseline characteristics will be assessed separately for these two index dates. For PCV13 unvaccinated patients, multiple eligible times may be identified within the study period, but only the first eligible time will be selected due to the large sample size of the unvaccinated cohort. Individuals who remain unvaccinated throughout the entire follow-up period can contribute a maximum of 1 time segment, which will be attributed to the unvaccinated cohort. All analyses will be conducted based on time-segment level data, which allows the exposure variable – PCV13 vaccination – to be treated as time-invariant within each segment.

The index date for the vaccinated cohort is defined as the date of first PCV13 vaccination. For the unvaccinated cohort, the index date is defined as the date of the first available healthcare claim that occurs after the eligibility date (September 14, 2014) and ensures a six-month period of continuous enrollment prior to the index date. Eligible vaccinated and unvaccinated index dates are 1) between September 14, 2014 and November 30, 2019 and 2) after the individual has at least 6 months of continuous enrollment in Medicare FFS Parts A and B. The 6 months of continuous enrollment prior to the index date for each time segment will be used as the baseline period. Baseline covariates, including demographics, preventative care behaviors, and comorbidities will be assessed during this period.

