# 9.2.2. Exclusion Criteria

Patients meeting any of the following criteria as of the index date will not have the respective time segment included in the study:

- 1. Evidence of PCV13 vaccination prior to the index date
- 2. Evidence of PPSV23 vaccination in the 365 days prior to the index datea
- 3.  $\geq 1$  diagnosis code for a high-risk condition in the 365 days prior to the index datea
- 4. Evidence of iatrogenic immunosuppression in the 6 months prior to the index date
- 5. Pneumonia diagnosis code in the hospital setting in the 365 days prior to the index datea
- 6. MACE diagnosis code in the hospital, SNF, or LTCF setting in the 365 days prior to the index datea
- 7. Medicare Part C enrollment between September 14, 2014 and the index date
- 8. PCV13 vaccinated individuals with a pneumonia diagnosis code in the hospital setting or a MACE diagnosis code in the hospital, SNF, or LTCF setting in the 13 days after first PCV13 vaccination

a. For adults with  $\geq 6$  months, but less than 365 days of prior continuous enrollment, the exclusion criteria will be evaluated during the continuous enrollment period that the adult has available.

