# 9.3.2. Outcomes

# Table 2.Outcome Variables

Variable	Role	Operational definition	Measurement period
Any MACE	Outcome	
 
≥1 International Classification of Diseases, Ninth Revision, Clinical Modification (ICD-9-CM) or International Classification of Diseases, 10th revision, Clinical Modification (ICD-10-CM) diagnosis code for myocardial infarction, stroke, or heart failure in the hospital, SNF, or LTCF setting.
 
Analyses include first event only and the code must occur one of the following time periods:
 
1. ≥0 days after the unvaccinated index date and before the minimum date of censoring for the unvaccinated time segment
 
2. ≥14 days after the vaccinated index date and before the minim date of censoring for the vaccinated time segment.
 
	Follow-up

PFIZER CONFIDENTIAL

CT24-WI-GL02-RF02 6.0 Non-Interventional Study Protocol Template For Secondary Data Collection Study Page 21 of 53

		ICD-9-CM or ICD-10-CM codes are listed in Appendix Table 2.	
Myocardial infarction	Outcome	≥1 ICD-9-CM or ICD-10-CM diagnosis code for myocardial infarction in the hospital, SNF, or LTCF setting.	Follow-up
		Analyses include first event only and the code must occur one of the following time periods:	
		
 
≥0 days after the unvaccinated index date and before the minimum date of censoring for the unvaccinated time segment
 
	
		
 
≥14 days after the vaccinated index date and before the minim date of censoring for the vaccinated time segment.
 
	
		ICD-9-CM or ICD-10-CM codes are listed in Appendix Table 2.	
Stroke	Outcome	≥1 ICD-9-CM or ICD-10-CM diagnosis code for ischemic stroke in the hospital, SNF, or LTCF setting.	Follow-up
		Analyses include first event only and the code must occur one of the following time periods:	
		
 
≥0 days after the unvaccinated index date and before the minimum date of censoring for the unvaccinated time segment
 
	
		
 
≥14 days after the vaccinated index date and before the minim date of censoring for the vaccinated time segment.
 
	
		ICD-9-CM or ICD-10-CM codes are listed in Appendix Table 2.	
Stroke sensitivity	Outcome	≥1 ICD-9-CM or ICD-10-CM diagnosis code for ischemic or hemorrhagic stroke in the hospital, SNF, or LTCF setting.	Follow-up

CT24-WI-GL02-RF02 6.0 Non-Interventional Study Protocol Template For Secondary Data Collection Study Page 22 of 53

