# 9.3.3. Mediation

### Table 3.Mediation Variables

Variable	Role	Operational definition	Measurement period
Community-acquired pneumonia (CAP)	Mediator	
 
≥1 ICD-9-CM or ICD-10-CM diagnosis code for CAP in any setting, where there were no hospital admissions or ventilator use within the 30 days prior.
 
CAP with be categorized as having 0 or ≥1 CAP event. Individuals will be classified as having ≥1 CAP event if there is at least one diagnosis code for CAP during one of the following time segments:
 
1. ≥0 days after the unvaccinated index date and before the minimum date of censoring for the unvaccinated time segment
 
2. ≥14 days after the vaccinated index date and before the minimum date of censoring for the vaccinated time segment.
 
ICD-9-CM and ICD-10-CM codes are listed in Annex 1.
 
	Follow-up
Community-acquired pneumonia (CAP) sensitivity	Mediator	
 
≥1 ICD-9-CM or ICD-10-CM diagnosis code for CAP in the hospital setting, where there were no hospitalizations or ventilator use in the 30 days prior the hospital admission associated with the CAP diagnosis.
 
For individuals with multiple CAP diagnosis codes during the 1-year follow-up period, CAP will be classified as the highest level of care associated with a CAP diagnosis code.
 
CAP with be categorized as having 0 or ≥1 CAP event. Individuals will be classified as having ≥1 CAP event if there is at least one diagnosis code for
 
	Follow-up

PFIZER CONFIDENTIAL

CT24-WI-GL02-RF02 6.0 Non-Interventional Study Protocol Template For Secondary Data Collection Study Page 25 of 53

CAP during one of the following time segments:

 
≥0 days after the unvaccinated index date and before the minimum date of censoring for the unvaccinated time segment
 

 
4. ≥14 days after the vaccinated index date and before the minimum date of censoring for the vaccinated time segment.
 

ICD-9-CM and ICD-10-CM codes are listed in Annex 1.

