# 9.3.4. Censoring

### Table 4.Censoring Variables

Variable	Role	Operational definition	Measurement period
Outcome under study	Censoring	See outcome table above. Table 2.	Follow-up
Disenrollment	Censoring	The month an individual disenrolls from the insurance plan, as indicated in the Master Beneficiary Summary File. Disenrollment date is calculated as the maximum date of enrollment.	Follow-up
Death	Censoring	Date of death reported in the database.	Follow-up
End of study period	Censoring	December 31, 2019	Follow-up
End of follow-up	Censoring	365 days after the index date for the 1- year analysis and 1095 days after the index date for the 3 year analysis.	Follow-up
PPSV23 receipt	Censoring	1 CPT or NDC code for PPSV23 vaccination during follow-up.	Follow-up
PCV13 receipt	Censoring	1 CPT or NDC code for PCV13 receipt during unvaccinated follow-up.	Follow-up
		1 CPT or NDC code for receipt of a second PCV13 vaccine during vaccinated follow-up.	

PFIZER CONFIDENTIAL

CT24-WI-GL02-RF02 6.0 Non-Interventional Study Protocol Template For Secondary Data Collection Study Page 26 of 53

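### The unvaccinated index claim can itself be a counted MACE, while vaccinated segments must be event-free for 13 days and count from day 14; together these rules favour apparent protection

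*Protocol*

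**What the plan says.** **Index date.** Protocol Section 9.1: "For the unvaccinated cohort, the index date is defined as the date of the first available healthcare claim that occurs after the eligibility date". Six months of prior enrollment are needed, but claim type and setting are not restricted, so a hospital admission qualifies.

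**Exclusions.** Section 9.2.2, nos. 5 and 6, remove hospital pneumonia and hospital, SNF or LTCF MACE in the 365 days before index. Day 0 is not covered. No. 8 applies to vaccinated segments only. It removes those with hospital pneumonia or "a MACE diagnosis code in the hospital, SNF, or LTCF setting in the 13 days after first PCV13 vaccination".

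**Outcome counting.** In Table 2, unvaccinated events count "≥0 days after the unvaccinated index date and before the minimum date of censoring for the unvaccinated time segment"; vaccinated events count "≥14 days after the vaccinated index date and before the minim date of censoring for the vaccinated time segment". The same pair of windows is in every outcome row, including the negative controls. Table 3 counts the CAP mediator "≥0 days after the unvaccinated index date" as well.

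**Clock and horizon.** Section 9.1 and the follow-up row of Table 2 start vaccinated follow-up 14 days after vaccination. Table 4 ends follow-up in both cohorts 365 days after index, or "1095 days after the index date for the 3 year analysis".

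Section 9.2 justifies the 14-day rule by the time the vaccine needs to become fully effective. It gives no reason for starting the comparator at day 0.

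**The concern.** A person whose first qualifying claim is a MACE admission passes the exclusions, enters the unvaccinated cohort on that day and contributes an event with no time at risk. No vaccinated segment can do so: a MACE in the following 13 days removes it, and one dated on the vaccination day is not counted. Events that cluster shortly after a claim-triggered index also count in one cohort only.

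Eligibility, time zero and counting therefore depend on exposure in a study that Section 9.1 describes as a target trial emulation. The extra events fall on the unvaccinated side, in the direction of the study hypothesis. IPTW balances baseline covariates and cannot remove an event counted on the index day. The three sensitivity analyses (Fine-Gray, stroke definition, hospital CAP) leave the start rule unchanged. With about 25 million eligible adults, even a small distortion would be statistically significant.

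**Working it through.** **Inputs.** From Section 9.5: 5-year event probability 21.2%, allocation 2:3, planning HR 0.85, control hazard 0.0507 per year. Not in the protocol, so assumed: the rate c of other claim-days per person-year, taken as 6, 12, 24 and 52.

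**1. The plan's hazard.** Solving 0.4(1 − exp(−5 × 0.85h)) + 0.6(1 − exp(−5h)) = 0.212 gives h = 0.0507, as stated.

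**2. Share of index claims that are a MACE.** p = 0.0507/(0.0507 + c). For c = 6: 0.0507/6.0507 = 0.84%.

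**3. Ratio with no true effect, day-0 events counted.** Let A = (1 − p)(1 − exp(−0.0507T)). Unvaccinated events are p + A, unvaccinated person-time is A/0.0507 and the vaccinated rate is 0.0507, so the rate ratio is A/(p + A). For c = 6 and T = 1: A = 0.99162 × 0.04944 = 0.04902, and 0.04902/(0.00838 + 0.04902) = 0.854. The large-sample Cox score equation, with the vaccinated clock starting at day 14, agrees:

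| c per year | p | Rate ratio, 1 y | Cox HR, 1 y | Cox HR, 3 y |
|---|---|---|---|---|
| 6 | 0.84% | 0.854 | 0.855 | 0.944 |
| 12 | 0.42% | 0.921 | 0.921 | 0.971 |
| 24 | 0.21% | 0.959 | 0.959 | 0.985 |
| 52 | 0.10% | 0.981 | 0.981 | 0.993 |

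**4. The lag and 13-day exclusion alone.** With p = 0 the ratio is A/A = 1, and the Cox HR is 1.00 at both horizons. Vaccinated days before day 14 supply neither events nor person-time.

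**5. Early events without a day-0 event.** If the unvaccinated hazard is 2, 3 or 5 times higher in days 0–13 (assumed), the 1-year null HR is 0.96, 0.93 or 0.86.

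**6. Dependence on the model fit.** In a simulation of the 0.84% case (1 year, true HR 1), the HR was 0.84 with day-0 events counted. It was 0.99 with zero-length intervals dropped (log-HR standard error 0.01), and also 0.99 with time measured from index and vaccinated entry at day 14. This simulation did not include a raised early hazard.

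**7. Chance of a false protective result.** Take p = 0.2%, for which the 1-year Cox HR is 0.961. The event fraction is 0.4 × 0.04944 + 0.6 × (0.002 + 0.998 × 0.04944) = 0.0506, or about 1,392 events at N = 27,520. Then √(1,392 × 0.4 × 0.6) × |ln 0.961| = 0.73, and Φ(0.73 − 1.96) is about 11%. The same calculation gives 99% at 1 million and about 100% at 25 million.

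**8. Horizon.** Vaccinated segments have at most 365 − 14 = 351 or 1095 − 14 = 1081 days at risk. One-year risk is 1 − exp(−0.0507 × 351/365) = 4.76%, against 4.94% over 365 days, a ratio of 0.963.

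**9. After alignment.** With one start day, one event-free window and no countable index-day event, the null HR is 1.00 at both horizons.

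**The case against.** The strongest reply is that day-0 events may never reach the primary estimate. Section 9.7 fits the Cox model by a counting process, and a zero-length interval belongs to no risk set. Table 4 measures the horizon from index. If the model's time scale did the same, with vaccinated entry at day 14, unvaccinated events in days 0–13 would have no vaccinated comparators and would drop out of the HR. The follow-up row that starts the vaccinated clock at day 14 is labelled descriptive, and time-scale conventions are commonly left to the SAP. All of this stands as a limit on size. It does not remove the defect: the protocol defines these as events, and a primary result should not rest on how software treats zero-length intervals. If the vaccinated clock starts at day 14, early events after day 0 still count. The cumulative incidence curves remain exposed either way.

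A reader might infer that the 14-day lag creates immortal time; step 4 shows that it does not at constant hazard. A reader might infer that the rule by itself reproduces the planning HR of 0.85. That needs the lowest assumed claim rate, the shorter horizon and day-0 events entering the model. Nor does the 351-day window bias a proportional-hazards HR; it matters only when cumulative incidence is read at unequal durations. Exclusion 8 covers the 13 days after vaccination, not day 0.

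The negative controls share the day-0 and day-14 windows and might signal a problem. Exclusion 8 does not cover those outcomes, so they can neither measure nor correct the bias for acute MACE.

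**Conclusion.** The point holds. The protocol lets an admission serve as both unvaccinated study entry and a counted outcome, gives the vaccinated cohort the opposite treatment, and plans nothing that would correct it. The direction is toward apparent protection.

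The size is unknown. The null HR range of about 0.85 to 0.98 at 1 year and 0.94 to 0.99 at 3 years rests on the assumed 6 to 52 claim-days per year, one hazard and one claim rate for everyone, and day-0 events entering the model. If zero-length intervals are dropped and early hazard is not raised, the HR is near 1. Only any MACE was computed. CAP shares the day-0 rule, but the primary mediator covers any setting while exclusion 8 covers hospital pneumonia only, so these figures do not carry over to the mediation analysis.

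This should be settled before analysis. The index date, exclusions and outcome windows are fixed in the protocol, and Section 9.7 says that major changes to primary endpoint definitions would be reflected in an amendment.

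**What to change.** Use one rule in both cohorts:

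1. Do not let a claim carrying a hospital, SNF or LTCF MACE code, or a pneumonia code, be the unvaccinated index, and do not count index-day events.
2. Start follow-up and the counting of outcomes and CAP 14 days after index in both cohorts, among people still under observation.
3. Apply the event-free window of exclusion 8 (MACE or hospital pneumonia through day 13) to both.
4. Measure the 365-day and 1095-day horizons from that common start.

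Amend Sections 9.1 and 9.2.2 and Tables 2, 3 and 4, with matching edits where Section 9.2 and the abstract repeat these rules. Pharmacy claims should not be used to set the index, because eligibility requires only Parts A and B. Death, disenrollment or a censoring vaccination before day 14 needs no separate exclusion, since those people are no longer under observation.

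The cost is wording and programming, plus the loss of a small share of unvaccinated segments and early events. The rule does not remove any excess risk that lasts beyond day 13.

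### A MACE or pneumonia admission can open an unvaccinated segment and be counted as its outcome on day 0, which cannot happen in the vaccinated cohort

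*Protocol*

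**What the plan says.** **Index date.** For the unvaccinated cohort, Section 9.1 says "the index date is defined as the date of the first available healthcare claim that occurs after the eligibility date", subject to six months of prior enrollment. It does not restrict the type, setting or diagnosis of that claim. Where several dates qualify, "only the first eligible time will be selected due to the large sample size of the unvaccinated cohort". The vaccinated index is the first PCV13 claim.

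**Exclusions (Section 9.2.2).** Criterion 6 removes segments with a "MACE diagnosis code in the hospital, SNF, or LTCF setting in the 365 days prior to the index date". Criterion 5 does the same for hospital pneumonia. Both stop before the index date. Criterion 8 adds a 13-day screen after the index, but it covers only "PCV13 vaccinated individuals with a pneumonia diagnosis code in the hospital setting or a MACE diagnosis code in the hospital, SNF, or LTCF setting".

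**Outcome windows (Table 2).** Unvaccinated events count "≥0 days after the unvaccinated index date and before the minimum date of censoring for the unvaccinated time segment". Vaccinated events count "≥14 days after the vaccinated index date and before the minim date of censoring for the vaccinated time segment". Every outcome row has this pair of windows, including both negative controls, and Table 3 uses it for CAP. The follow-up row of Table 2 starts the unvaccinated clock at the index date and the vaccinated clock 14 days after vaccination.

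**The concern.** The contact that sets time zero can be the outcome in one cohort and not in the other. Someone whose earliest claim in the study period is an infarction admission enters the unvaccinated cohort on that day, has no disqualifying history, and contributes an event with essentially no time at risk. In the vaccinated cohort a vaccination claim sets the index, nothing before day 14 counts, and segments with early events are removed.

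This undoes the equal starting risk that Section 9.2 gives as the reason for excluding recent MACE and pneumonia, and it does not fit the target trial emulation described in Section 9.1. The direction favors the study hypothesis on the primary objective. Weighting on baseline covariates cannot remove an event that defines time zero in one cohort only. The negative controls use the same day-0 rule, so they might reveal the problem but would not correct it. For CAP, the mediator would be over-counted in the unvaccinated, which exaggerates the vaccine-to-CAP path.

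**Working it through.** **1. The plan's own figures.** Section 9.5 gives a 5-year event probability of 21.2%, a vaccinated share of 39.6% and an assumed HR of 0.85. With control hazard 0.0507, 0.396·exp(−5·0.85·0.0507) + 0.604·exp(−5·0.0507) = 0.788 = 1 − 0.212, so the stated hazard reproduces. The stated N of 27,520 at 1 year also reproduces (27,571 by the Lakatos log-rank method). The sample size is not in question here.

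**2. Can a day-0 MACE get through?**

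| Step | Unvaccinated | Vaccinated |
|---|---|---|
| Claim that sets index | any healthcare claim | PCV13 claim |
| Pre-index MACE/pneumonia exclusion | days before index | days before index |
| Post-index screen | none | 13 days after vaccination |
| Events count from | day 0 | day 14 |
| Clock starts | day 0 | day 14 |

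Yes, and only in the left-hand column.

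**3. Size if day-0 events are kept.** Let p be the share of unvaccinated index claims that are MACE, λ the MACE hazard, T the follow-up in years and q = 1 − exp(−λT). Assume no vaccine effect. The unvaccinated cohort has p + (1−p)q events over person-time (1−p)q/λ, so the vaccinated-to-unvaccinated rate ratio is

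R = 1 / [1 + p/((1−p)q)].

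The documents do not give p. As an assumption, let other claims arise at a constant rate of k per year. Then p = λ/(λ+k) and p/(1−p) = λ/k. With λ = 0.0507, q = 0.0494 at 1 year and 0.1411 at 3 years. For k = 6, for example, λ/k = 0.00845 and R at 1 year = 1/(1 + 0.00845/0.0494) = 0.85.

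| k per year | p | R, 1 year | R, 3 years |
|---|---|---|---|
| 6 | 0.84% | 0.85 | 0.94 |
| 10 | 0.50% | 0.91 | 0.97 |
| 20 | 0.25% | 0.95 | 0.98 |
| 40 | 0.13% | 0.975 | 0.99 |

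The 0.0507 hazard presumes an HR of 0.85. Under no effect the pooled hazard is −ln(0.788)/5 = 0.0477, which lowers p slightly (0.79% at k = 6) and leaves R unchanged to the precision shown.

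**4. Check with a Cox model.** An expected-score Cox calculation at hazard 0.0477 with p = 0.5% gives a 1-year HR of 0.903. A simulation of 400,000 segments gives 0.900 (95% CI 0.874 to 0.926) with day-0 events kept and 0.994 (0.966 to 1.024) with them removed.

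**5. Does a small bias matter at this scale?** The protocol expects about 25 million eligible adults. Events in 1 year are about 25,000,000 × (1 − exp(−0.0477)) ≈ 1.16 million. Ignoring weighting, the HR detectable with 80% power is exp(−(1.96 + 0.84)/√(1.16 million × 0.24)) ≈ 0.995. Even p = 0.1%, which gives a 1-year HR of 0.979, would almost surely be significant under no effect.

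**The case against.** **The hazard ratio may escape.** Section 9.7 specifies a counting-process Cox model. An event on the day the clock starts has an empty interval, and software that drops such records removes it from the HR, which is then 1.00 under no effect. Delayed entry at day 14 on a clock running from vaccination would have the same result. This stands, so it cannot be said that the primary HR is certainly biased. But the protocol states neither, Table 2 expressly counts day 0, and coding follow-up as days plus one would keep the events. Dropping the records in the Cox step would not protect a cumulative incidence curve that retains them, nor CAP, which is a yes/no variable entered in a logistic model.

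**The size is nearly all assumption.** This also stands. At 1 year R is close to 1/(1 + 1/k). If prescription claims count, k could be high and the bias small. At k = 4 it would be larger (0.80). A reader might infer from the first row of the table that the planned effect of 0.85 is merely this artefact, or that PCV13 will look protective when it is not. The documents support neither: they give no claim frequency, and nothing here shows that the true effect is null.

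**Days 1 to 13 are harmless.** Under a constant hazard, counting those days in one cohort adds no rate bias, because the person-time is counted too. The distortion comes from the event that creates the index. Still, moving the start only to day 1 would not be safe: Table 2 also accepts SNF and LTCF codes, so the same episode could be scored from post-acute claims a few days later.

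**It could be left to the SAP.** The windows are fixed in protocol Tables 2 and 3, and Section 9.7 says major changes to primary endpoint definitions require a protocol amendment.

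**Conclusion.** The asymmetry is in the text, and no other provision cures it. A MACE or pneumonia claim that creates the unvaccinated index is counted in that cohort, and nothing comparable can be counted in the vaccinated cohort. The direction is toward vaccine benefit wherever day-0 events are retained. For the Cox HRs this depends on coding that the protocol leaves unstated.

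The magnitude is a range, not an estimate: about 0.85 to 0.975 at 1 year and 0.94 to 0.99 at 3 years, assuming no true effect, constant hazards, 6 to 40 claims per year and day-0 events kept. The effects on the CAP mediator and the negative controls follow from the same rule but are not quantified. The rule should be changed before analysis, because even the mild end of the 1-year range exceeds what a cohort of this size can detect.

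**What to change.** 1. Apply criterion 8 to both cohorts: drop unvaccinated segments with hospital pneumonia, or hospital, SNF or LTCF MACE, on days 0 to 13 after index.
2. In every row of Tables 2 and 3, make the unvaccinated window start at 14 days or more after index instead of 0. This also handles non-hospital CAP and the negative controls, which the screen does not cover.
3. Start unvaccinated follow-up at day 14 in Section 9.1 and in the follow-up row of Table 2.

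Limiting the unvaccinated index to an ambulatory claim is an optional addition.

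**Cost.** Protocol wording, programming and a small loss of unvaccinated segments. For MACE the loss is roughly p plus 14 days of hazard (0.0507 × 14/365 = 0.19%): 0.84% + 0.19% = 1.0% at 6 claims per year and 0.28% + 0.19% = 0.5% at 18. Segments with early hospital pneumonia or censored before day 14 are lost in addition; the documents do not allow their number to be estimated. Against about 25 million eligible adults and a largest required N of 36,485, the MACE loss does not threaten power.
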